- 7. Untreated hypothyroidism
- 8. Hyperprolactinemia
- 9. BMI \leq 17 and \geq 40
- 10. Uncorrected uterine anomaly
- 11. Women with osteoporosis
- 12. Women with moderate or severe hepatic impairment defined by Child-Pugh Classes B (moderate) and C (severe)
- 13. Women using strong CYP3A inhibitors (e.g. ketoconazole, clarithromycin)
- 14. Women at high risk of thromboembolic disorders including those that smoke, have cardiac valvular disease, atrial fibrillation, hypertension not controlled by medication, and a history of severe migraines.
- 15. Severe renal disease with GFR < 15 ml/min.

Sample Size

Based on previous studies (Likes et al., 2019) we calculated that 50 patients (25 per arm) are required to have a 90% chance of detecting, as significant at the 5% level, an increase in the primary outcome measure from 11% live birth in the OCP group to 50% in the elagolix group. We decided to include 50 subjects per treatment arm (elagolix 200 mg BID vs OCPs) for 2 months, because unlike the Likes study, we are not using a no treatment control arm, and OCPs may have some benefit over no treatment. Having a non-randomized, no treatment control group to follow will allow us some flexibility, however, in comparing outcomes over time.

Enrollment may vary between sites, but we hope to recruit approximately 1/2 of the subjects at our site with the remainder at each of the other 2 sites (UNC and Stanford). We will perform interim analyses after 25 subjects per arm for safety assessment. Based on the 12 months of treatment in the original study (Taylor et al., 2017), safety concerns are minimal. Nevertheless, we will halt the study using the following stopping rules:

- 1) If after 25 subjects per arm, the OCP ongoing pregnancy rate is higher than the treatment arm with elagolix
- 2) There is no difference between the no treatment controls and the elagolix treatment are at 25 patients per arm

We will perform an interim analysis after 25 subjects per arm to recalculate sample size requirements based on the outcomes at that point (Kuman and Chakraborty 2016).

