Visit 5: Completion of the study. Patients will return periodically for standardized treatments as part of their FET cycle for endometrial preparation, ultrasound and embryo transfer as dictated by the clinicians in the practice. Outcomes will be recorded and extracted from their SART database for pregnancy included extended follow-up for live birth rate.

Patients experiencing unanticipated problems with the protocol or who experience adverse events such that they do not tolerate the treatment they are assigned, will be allowed to discontinue treatment and be provided the opportunity to use the other treatment if they so choose. The outcomes of such cycles would be collected separately and included as observational data only and not included in the randomized data analysis. Alternatively, they can simply drop out of the study and resume medical therapy as appropriate or pursue frozen embryo transfer as previously planned.

Outcome Variables

The following outcome data will be collected on each subject:

- 1) BCL6/SIRT1 HSCOREs
- 2) hCG level (first)
- 3) Progesterone levels at first hCG measurement (ng/dl)
- 4) hCG level (second)
- 5) Pregnancy outcome (not pregnant, pregnant biochemical, pregnant miscarriage, pregnant ectopic, pregnant ongoing, pregnant delivered, pregnant 2nd or 3rd trimester loss)
- 6) Categorical outcome (pregnant/not pregnant; summary designation)
- 7) Comments related to overall outcomes
- 8) Number of sacs (0, 1, 2, 3)

Independent Variables

The following demographic data will be collected on each subject:

- 1) Age (based on date of birth)
- 2) Weight
- 3) BMI
- 4) Gravidy/Parity
- 5) Randomization group (elaglox, OCPs, non-randomized control)
- 6) Embryo grade
- 7) Number of remaining euploid embryos
- 8) PGT-A results (narrative)
- 9) Endometrial thickness
- 10) Peak estradiol levels (pg/dl)
- 11) Comments regarding embryo transfer
- 12) Embryo transfer physician (name)
- 13) Number of embryos transferred (confirm that 1 was transferred)

Analytical Plan

Statistical analysis: Statistical analyses will be performed using the Student's ttest for data from the two groups. All data will be presented as means \pm SEM. p < 0.05 was considered statistically significant. Fisher's exact test, relative risk, and 95% confidence interval (CI) will be used for comparisons of categorical data.

Independent Variables.

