Measurement of hormones. Estrogen, progesterone and hCG assays will be run by the hospital's clinical laboratories using a competitive antibody technology. Venous blood will be drawn into serum separator tubes and taken immediately to the clinical lab for processing (available 24 hours per day).

Results will be analyzed initially using descriptive statistics. Comparison between groups will be done using chi square tests for proportions, and t-tests for continuous variables. Regression analysis will be performed to identify independent outcome predictors. Other inferential statistical analysis will be conducted as appropriate.

Human Subjects Protection

Subject Recruitment Methods

Subjects who failed IVF or FET with a previous endometrial biopsy showing elevated endometrial BCL6 and SIRT1 will be identified as part of ongoing care. We do not discriminate on the basis of race or economic status, although we do have age and BMI cut-off criteria defined in the protocol. Subjects will be approached in the privacy of the clinic and all conversations will be confidential.

- We plan to use a recruitment flyers in the clinic to help motivate and identify willing subjects. A copy of this poster is provided with the submission material for IRB review.
- Privacy will be protected and no records kept until subjects/patients agree to participate in the study?
- If an individual declines participation including randomization any and all documents will be destroyed.

Informed Consent

Signed informed consent will be obtained from each subject by her physician or a clinic research nurse. Consent will be obtained in the CFEM clinical space where patients receive their care from the REI unit. Other centers will use clinical research staff to consent patients in private offices under similar conditions.

Confidentiality and Privacy

Confidentiality will be protected by collecting only information needed to assess study outcomes, minimizing to the fullest extent possible the collection of any information that could directly identify subjects, and maintaining all study information in a secure manner. To help ensure subject privacy and confidentiality, only a unique study

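### Does naming both Fisher's exact test and chi-square for the live-birth comparison, with no power quoted at 50 per arm, undermine the primary analysis?

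*Combined protocol and SAP*

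**What the plan says.** The Design section makes live birth rate, a yes/no outcome, primary. Two places then name a test that covers it.

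- Analytical Plan, statistical analysis paragraph: Fisher's "exact test, relative risk, and 95% confidence interval (CI) will be used for comparisons of categorical data".
- The general results paragraph that follows the description of hormone assays: "Comparison between groups will be done using chi square tests for proportions, and t-tests for continuous variables".

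Neither sentence mentions live birth, states precedence, or says whether chi-square is continuity-corrected. Two-sided P values are specified only under Visit 3, in the adverse-event text.

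The Sample Size section opens "Based on previous studies", citing one earlier study, and continues: "we calculated that 50 patients (25 per arm) are required to have a 90% chance of detecting, as significant at the 5% level", a rise "from 11% live birth in the OCP group to 50% in the elagolix group". It then enlarges the trial: "We decided to include 50 subjects per treatment arm". The reason given is that, unlike the cited study, "we are not using a no treatment control arm, and OCPs may have some benefit over no treatment". No power is quoted at 50 per arm. An interim look after 25 per arm is to recalculate the sample size from observed outcomes.

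**The concern.** Two tests for one primary comparison look like a contradiction, and the trial is open-label. If a result is borderline, someone could choose the test after seeing the table. For example, 25/50 against 15/50 is significant by uncorrected chi-square and not by Fisher.

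The sample-size claim also seems to depend on the unnamed test, because 90% at 25 per arm does not hold under two-sided Fisher. The plan doubles the trial because OCPs may do better than 11%, yet does not show what 50 per arm achieves if they do. Finally, the 11% is labelled as an OCP rate, although the section says that the cited study had an untreated control.

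At stake would be the verdict on a borderline primary result, the outcome of the interim recalculation, and the reader's view of how robust the trial is.

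**Working it through.** **Inputs.** From Sample Size: 11% versus 50% live birth, 5% level, 90% power, 25 per arm calculated, 50 per arm planned. Two-sided testing is taken from Visit 3. OCP rates above 11%, and 45 per arm analysed, are assumptions.

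**1. The plan's own figure.** Normal approximation with unpooled variance:

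n = (z₀.₉₇₅ + z₀.₉₀)² × [p₁(1−p₁) + p₂(1−p₂)] / (p₂−p₁)²

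= (1.960 + 1.282)² × (0.0979 + 0.2500) / 0.39²

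= 10.51 × 0.3479 / 0.1521 = 24.0, rounded up to 25.

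The stated 25 per arm is reproduced.

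**2. Exact power at 25 per arm.** Power is the sum, over all pairs (a, b) that the test rejects, of Bin(a; n, p₁) × Bin(b; n, p₂). For 11% versus 50%:

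- uncorrected chi-square 89.1%
- two-sided Fisher 80.3%
- one-sided Fisher 89.1%

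Exact power first reaches 90% at 26 per arm for chi-square and 31 for Fisher. The quoted 90% therefore fits chi-square. The planned 50 exceeds both 26 and 31.

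**3. Exact power at 50 per arm, elagolix 50%, no losses.**

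| OCP rate | Chi-square | Fisher | Tests disagree |
|---|---|---|---|
| 11% (plan) | 99.5% | 99.0% | 0.4% |
| 18% (assumed) | 93.4% | 90.4% | 3.0% |
| 20% (assumed) | 89.5% | 85.3% | 4.2% |
| 25% (assumed) | 74.5% | 67.5% | 7.0% |
| 30% (assumed) | 54.6% | 46.4% | 8.2% |

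Participants who switch treatment are "included as observational data only and not included in the randomized data analysis", so fewer than 50 per arm may be analysed. With 45 per arm, power at 11% versus 50% is 99.0% by chi-square and 98.1% by Fisher.

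**4. What free choice of test could do.** At 50 per arm, uncorrected chi-square rejects 94 tables that Fisher does not, and Fisher rejects none that chi-square does not. Continuity-corrected chi-square rejects exactly Fisher's tables at this size. So picking the better P value is identical to using uncorrected chi-square. Exact size over common null rates of 11% to 50%:

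- uncorrected chi-square 4.9% to 5.7%
- Fisher 1.9% to 3.5%

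**5. A borderline table, 25/50 against 15/50.**

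- Uncorrected χ² = 100 × (25×35 − 15×25)² / (50×50×40×60) = 100 × 500² / 6,000,000 = 4.17, P = 0.041.
- Corrected χ² = 100 × (500 − 50)² / 6,000,000 = 3.375, P = 0.066. Fisher also gives P = 0.066.
- Relative risk = 25/15 = 1.67. On the log scale SE = √(1/25 − 1/50 + 1/15 − 1/50) = 0.258, so the 95% CI is exp(0.511 ± 1.96 × 0.258) = 1.00 to 2.76.

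The estimate and interval promised in the Analytical Plan are the same whichever test supplies the P value, and they show the result to be borderline.

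**The case for a change.** The strongest case for a change has three parts.

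**The test affects the recalculation.** With OCP at 20% and elagolix at 50%, 90% power needs 51 per arm by chi-square and 58 by Fisher, a difference of 2 × 7 = 14 participants. In an open-label trial the test is better fixed before outcomes are seen. This is correct. But both answers come from acceptable tests, and the 20% is assumed. The observed rates that drive a recalculation from 25 per arm are themselves very uncertain.

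**Power falls quickly as the OCP rate rises.** At 30% it is near one half under either test, and a higher OCP rate is the plan's own reason for enlarging the trial. This is also correct. It does not come from the conflict between tests, though, and would remain if one test were named. The document gives no OCP rate above 11%, so any grid is the reader's own. It also holds elagolix at 50%: at an assumed 40%, power against OCP 20% is 60% by chi-square and 52% by Fisher. The plan acknowledges the uncertainty by doubling the size and scheduling a recalculation.

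**The 11% appears to be an untreated-control rate carried over to OCPs.** That reading is plausible, but the source is not available here. The Sample Size section itself names the difference in control arms and enlarges the trial because of it.

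What stands is that the document would be tidier with one named test and a power figure at the planned size.

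**Conclusion.** The two sentences do name different tests for the same comparison, and power at 50 per arm is not stated. Neither calls for a change. Both tests are standard for a two-arm comparison of proportions. The worst result of leaving the choice open is a test with size 4.9% to 5.7% instead of 5%. At the plan's own rates the choice alters the verdict in 0.4% of trials, and power is at least 99% either way.

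The 90% quoted at 25 per arm is reproduced by the usual formula and agrees with uncorrected chi-square. It would be about 80% only under two-sided Fisher, and the planned 50 per arm exceeds what either test needs at those rates. An analyst who follows either sentence, and reports the promised relative risk with its interval, reaches a sound conclusion.

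This rests on two-sided testing, 50 analysed per arm (45 gives nearly the same), and the stated 11% and 50%. If the OCP rate were 20% to 30%, the tests would disagree in 4% to 8% of trials, and the low power itself would matter far more than which test was used.
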